# 2. STUDY OBJECTIVES AND ENDPOINTS

OBJECTIVES	ENDPOINTS
Primary  To assess the safety and tolerability of single and multiple ascending oral doses of SBP-9330	Incidence and severity of adverse events     (AEs) for subjects administered SBP-9330
in healthy nonsmokers and healthy smokers	
 
compared to placebo
 
Changes in vital signs, physical examination findings, ECG findings,
 
C-SSRS questionnaire results, and clinical laboratory results for subjects administered
 

	SBP-9330 compared to placebo
Secondary	
To determine single and multiple oral dose	Single Ascending Dose (SAD) Phase
pharmacokinetics (PK) of SBP-9330 in healthy nonsmokers and healthy smokers	The main PK endpoints for the SAD phase are the following PK parameters:
	Multiple Ascending Dose (MAD) Phase
	The main PK endpoints for the multiple ascending dose (MAD) phase are the following PK parameters:
	$ \begin{array}{cccccccccccccccccccccccccccccccccccc$
	For all study phases, additional PK parameters (as noted in Section 8.4) may be estimated as appropriate to support the main PK endpoints.
To explore the effect of food on the single oral dose PK of SBP-9330 in healthy nonsmokers	The main PK endpoints to assess the effect of food after a single oral dose of 600 mg SBP-9330 to healthy nonsmokers are the following:
	C max , AUC 0-t , and AUC 0-∞ ; T max will also be evaluated
	Additional PK parameters may be estimated as appropriate to support the main PK endpoints (Section 8.4).
Exploratory	
To explore the effect of SBP-9330 on smoking-related assessments	Expired carbon monoxide (ECO) level
	Plasma cotinine level
	Number of cigarettes smoked (smoking log)
	Minnesota Nicotine Withdrawal Scale     (MNWS) responses

OBJECTIVES	ENDPOINTS
	Questionnaire on Smoking Urges – Brief version (QSU-Brief) responses

Altasciences Project Number: CNO-P5-319

## 3. STUDY DESIGN

## 3.1. Adaptive Features and Risk Management of Study Design

The rationale for the following adaptive features is based on taking an iterative, hypothesis-forming approach in this clinical trial. The following categories will be adapted as shown in Table 6.

**Table 6** Adaptive Features and Boundaries

Adaptive study design category	Adaptive Features	Boundaries
Dose level for the SAD cohorts	SAD dose levels may be adjusted based on safety and available PK data reported in the previous cohort(s).	Doses are intended to escalate; however, they may be adjusted to an intermediate (lower) or equivalent dose, based on safety and available PK data reported in the previous cohort(s).  Escalation from one dose level to the next dose level will not be more than 3-fold the previous dose.
Dose level for the MAD cohorts	Doses for the MAD cohorts will be adapted in accordance with safety and available PK data collected in previous cohorts during the SAD or MAD phase.	The first MAD dose must be lower or equal to a dose administered in a SAD cohort for which safety and PK data are available.  Doses are intended to escalate; however, they may be adjusted to an intermediate (lower) or equivalent dose, based on safety and available PK data reported in the previous cohort(s).  Escalation from one dose level to the next dose level will not be more than three-fold the previous dose.  A MAD daily dose level cannot be higher than the highest dose level tested in SAD.
Dose level for the Smoker cohorts	Smoker cohort dose levels will be adapted in accordance with safety and available PK data collected in previous cohorts during the SAD or MAD phase.	The first Smoker dose must be lower or equal to a dose administered in a MAD cohort for which safety and PK data are available.  Doses are intended to escalate; however, they may be adjusted to an intermediate (lower) or equivalent dose, based on safety and available PK data reported in the previous cohort(s).  Escalation from one dose level to the next dose level will not be more than three-fold the previous dose.  A Smoker cohort daily dose level cannot be higher than the highest dose level tested in the MAD phase.
Dosing frequency for the MAD and Smoker cohorts	The dosing frequency may be modified from once daily to twice daily.	The modification from once daily to twice daily administration will not change the total daily dose outlined in this protocol.
The quantity of cohorts in each phase (SAD or MAD)	The quantity of cohorts may be decreased.	The maximum number of cohorts for the SAD and MAD phase are 5 and 4, respectively.  The number of cohorts in each phase may be decreased at the discretion of the Sponsor

Altasciences Project Number: CNO-P5-319

Adaptive study design category	Adaptive Features	Boundaries
		depending on the emerging safety and PK data from the previous cohorts.
The quantity of cohorts during the Smoker phase	A 3 rd cohort may be added.	The Smoker phase will have a maximum of 3 cohorts. There are 2 planned cohorts and an additional cohort may be added depending on the emerging PK and safety data in the previous cohorts.
Overlap between SAD and MAD phases	The MAD phase of the study may commence in parallel to the SAD or thereafter.	The decision on how early the MAD phase of the study may start and the doses to be administered will be determined by the Sponsor after consultation with the DSMB based on emerging safety and PK data.  A MAD dose level cannot be higher than the last dose level administered in the SAD phase.
Blood collection during the MAD phase	The PK blood sampling timepoints during the MAD phase may be modified.	Depending on data obtained during the SAD phase, the PK sampling timepoints during the MAD phase may be modified in order to optimize characterization of PK parameters of interest.
Food-Effect cohort	The food-effect cohort may be done in a cohort with a dose level other than 600 mg.	Depending on data obtained in the previous cohorts, the food-effect may be evaluated at a dose level other than 600 mg to optimize characterization of PK parameters of interest.

Abbreviations: DSMB = Data and Safety Monitoring Board; MAD = multiple ascending dose;

PK = pharmacokinetic; SAD = single ascending dose

The decision-making process for the above adaptive study categories will be as follows, unless otherwise stated:

- Interim review of safety and emerging PK data for SBP-9330 from completed or ongoing SAD, MAD, or Smoker cohorts in a blinded fashion by the Data and Safety Monitoring Board (DSMB). For Part C (Smoker Phase), the DSMB will be provided the randomization code to aide in the review of safety and PK data.
- Outcome on the adaptive study category will be documented by the DSMB.

Based on the above, progression to the next dose cohort may be performed without delay (i.e., without prior approval from the Institutional Review Board (IRB) or regulatory authorities), unless the adaptive features are outside of the pre-specified boundaries. If it is anticipated to progress with adaptive features outside of the pre-specified boundaries, prior approval must be granted by the IRB and regulatory authorities.

#### 3.2. Data and Safety Monitoring Board (DSMB)

A DSMB will be established to assure that the safety of the study subjects is protected while the scientific goals of the study are being met. Specifically, the DSMB is charged with monitoring the safety of participants and the quality of the data, as well as the appropriate termination of studies when risks have been uncovered or when it appears that the clinical trial cannot be

Altasciences Project Number: CNO-P5-319

concluded successfully. The DSMB is responsible for reviewing and evaluating safety and available plasma PK data collected after each cohort.

The DSMB will be comprised of voting members who are independent of the Sponsor and CRU and will, at a minimum, include physicians experienced in drug safety. The composition and operations of the DSMB will be detailed in a separate document that will serve as the Data and Safety Monitoring Plan (DSMP).

The DSMB will review safety data up to discharge and available plasma PK data of all the subjects in the respective cohort in a blinded manner to provide recommendations to the Sponsor and PI whether to escalate doses between cohorts. The minimum number of subjects required to decide on dose escalation is six subjects (i.e., at least four on active treatment) for Part A (SAD) and eight subjects (i.e., at least six on active treatment) for Parts B (MAD) and C (Smoker).

The DSMB will also advise as to when MAD dosing may commence and whether any stopping criteria were met. For Part A and Part B, these assessments will generally be made without breaking the blinded randomization code. For Part C, the DSMB will be provided the randomization code to aide in the review. If judged necessary by the DSMB, an individual or the complete cohort may be unblinded during evaluation of the study data. Before unblinding, a decision should be made about the action to be taken based on the revealed treatment allocation. The DSMB may adjust the dose based on the treatment-emergent safety and available PK data.

# 3.3. Overall Study Design

This is a single-center, first-in-human, randomized, double-blind, placebo-controlled, single- and multiple-dose escalating study incorporating a food-effect cohort.

The study will include 3 parts:

- Part A: SAD phase with a nested food-effect cohort
- Part B: MAD phase
- Parc C: Smoker phase

Each cohort will receive SBP-9330 in an ascending dose order or until stopping rules as outlined in Section 4.3.2 are met.

Part A – SAD phase with nested food-effect cohort will include approximately 40 subjects (5 cohorts of 8 subjects), Part B – MAD phase will include approximately 40 subjects (up to 4 cohorts of 10 subjects), and Part C – Smoker phase will include approximately 30 subjects (up to 3 cohorts of 10 subjects). Therefore, up to 110 subjects will be included in the study.

All subjects who complete the study and those terminating early will be required to complete the End of study (EOS)/Follow up procedures.

The End of Trial will correspond to the last patient last visit of the study.

#### 3.3.1. Part A – SAD Phase with Nested Food-Effect Cohort

Screening of participants will occur within approximately 28 days of the first scheduled administration of study medication. Screening data will be reviewed to determine subject eligibility. Subjects who meet all inclusion criteria and none of the exclusion criteria and who

Altasciences Project Number: CNO-P5-319

consent to participation will be admitted to the CRU for baseline evaluations before dosing (Day -1). All baseline safety evaluation results should be available prior to dosing and continued eligibility confirmed. Subjects in Cohort A3 will have eligibility confirmed for Day -1 for fasted dose (Period 1) only and not for the fed dose (Period 2).

Eligible subjects will be randomized to SBP-9330 or placebo in 1 of the 5 ascending dose cohorts (8 subjects per cohort) to have a total of 6 subjects receiving SBP-9330 and 2 subjects receiving placebo. All cohorts in the fasting state will be dosed according to a sentinel dosing design to ensure optimal safety. Initially, 2 subjects will be dosed; 1 subject will be dosed with SBP-9330 and 1 subject with placebo. If the safety and tolerability results of the first 24 hours following dosing for the initial subjects are acceptable to the Investigator, the other 6 subjects (5 active and 1 placebo) may be dosed approximately 24 hours after dosing of the sentinel group.

Furthermore, one single-dose, two-period, crossover, food-effect cohort will be integrated into a SAD cohort (Cohort A3).

The proposed SAD design and planned escalation are presented in Table 7.

Altasciences Project Number: CNO-P5-319

Table 7 Part A – SAD Phase with Nested Food-Effect Cohort Design and Dose Levels

Cohort	N (active:placebo)	Dose (mg)	Drug administration
A1	6:2 (1:1 [sentinel group] and 5:1 [remaining subjects])	150 mg (1 × 150-mg SBP-9330 capsule or matched placebo)	Single oral dose administration of SBP-9330 or placebo under fasting conditions on Day 1.
A2	6:2 (1:1 [sentinel group] and 5:1 [remaining subjects])	300 mg (1 × 300-mg SBP-9330 capsule or matched placebo)	Single oral dose administration of SBP-9330 or placebo under fasting conditions on Day 1.
A31	6:2 (1:1 [sentinel group] and 5:1 [remaining subjects] for Period 1 only)	600 mg (2 × 300-mg SBP-9330 capsule or matched placebo)	Single oral dose administration of SBP-9330 or placebo under fasting conditions on Day 1 of Period 1 and fed conditions on Day 1 of Period 2. Washout between the 2 periods will be at least 7 to 14 days.
A4	6:2 (1:1 [sentinel group] and 5:1 [remaining subjects])	1200 mg (4 × 300-mg SBP-9330 capsule or matched placebo)	Single oral dose administration of SBP-9330 or placebo under fasting conditions on Day 1.
A5	6:2 (1:1 [sentinel group] and 5:1 [remaining subjects])	2400 mg (8 × 300-mg SBP-9330 capsule or matched placebo)	Single oral dose administration of SBP-9330 or placebo under fasting conditions on Day 1.

<sup>12-period, food-effect cohort

For Cohorts A1, A2, A4, and A5, each subject will receive the assigned treatment (SBP-9330 or placebo) under fasting conditions.

For Cohort A3 (2 period food-effect cohort), each subject will receive the randomly assigned treatment (SBP-9330 or placebo) under fasting conditions in Period 1. After a 7- to 14-day washout period, they will receive the same single dose of SBP-9330 or placebo in a fed state in Period 2, 30 minutes after the start of an FDA High-Fat and High-Calorie Breakfast. Escalation to Cohort A4 will be based only on the fasting period safety and PK and may proceed in parallel to the A3 fed period.

All cohorts in the fasting state will be dosed according to a sentinel dosing design to ensure optimal safety. Initially, 2 subjects will be dosed; 1 subject will be dosed with SBP-9330 and 1 subject with placebo. If the safety and tolerability results of the first 24 hours following dosing for the initial subjects are acceptable to the Investigator, the other six subjects (5 active and 1 placebo) may be dosed approximately 24 hours after dosing of the sentinel group.

Altasciences Project Number: CNO-P5-319

Escalation to the next higher dose will only proceed if none of the stopping criteria have been reached and when the safety and tolerability and plasma PK analysis of the previous dose, including delayed emergence of significant AEs in earlier cohorts, are acceptable to the Investigator, Sponsor and DSMB.

The SAD phase will have a maximum of 5 cohorts. The number of cohorts may be changed at the discretion of the Sponsor depending on the emerging safety and plasma PK data from the previous cohorts. The dose levels proposed for SAD cohorts may be adjusted during the course of the study based on preliminary safety and plasma PK data but escalation will not be more than 3-fold the previous dose.

## For Cohorts A1, A2, A4, and A5:

- Subjects will be confined to the CRU from at least 10 hours prior to drug administration until approximately 48 hours after study drug administration. Subjects will therefore be confined for 4 days and 3 nights (Day -1 to Day 3). However, they may be advised to stay longer at the CRU for safety reasons, if judged necessary by an Investigator.
- Subjects will return for a follow-up visit approximately 5 days after the last PK blood sample/discharge (Day 8±1).
- Total study duration: up to 38 days (including Screening)

## For Cohort A3 (food-effect cohort):

- In each period, subjects will be confined to the CRU from at least 10.5 hours prior to drug administration until approximately 48 hours after study drug administration. Subjects will therefore be confined for 4 days and 3 nights (Day -1 to Day 3) in each period. However, they may be advised to stay longer at the CRU for safety reasons, if judged necessary by an Investigator.
- Washout period between treatment administrations: at least 7 to 14 calendar days
- Subjects will return for a follow-up visit approximately 5 days after the last PK blood sample/discharge (Day 8±1) of Period 2.
- Total study duration: up to 46 days (including Screening)

The schedule of activities of the SAD Phase of the study is described in Table 1.

### 3.3.2. Part B - MAD Phase

Screening of participants will occur within approximately 28 days prior to the first scheduled administration of study medication. Screening data will be reviewed to determine subject eligibility. Subjects who meet all inclusion criteria and none of the exclusion criteria and who consent to participation will be admitted to the CRU for baseline evaluations before dosing (Day -1). All baseline safety evaluation results should be available prior to dosing and continued eligibility confirmed.

Subjects will be randomized to SBP-9330 or placebo in 1 of the 3 ascending dose cohorts (10 subjects per cohort in 4:1 [SBP-9330:placebo] ratio) to have a total of 8 subjects receiving SBP-9330 and 2 subjects receiving placebo. An additional MAD cohort (Cohort B4) may be

Altasciences Project Number: CNO-P5-319

added at the discretion of the Sponsor depending on emerging safety and PK data from previous cohorts.

The proposed MAD design and planned escalation are presented in Table 8.

Table 8 Part B - MAD Phase Design and Dose Levels

Cohort	N (active:placebo)	Dose	Drug administrations
B1	8:2	adaptive	Once daily oral administrations of SBP-9330 or placebo for 14 consecutive days (Days 1 to 14) under fasting conditions
B2	8:2	adaptive	Once daily oral administrations of SBP-9330 or placebo for 14 consecutive days (Days 1 to 14) under fasting conditions
В3	8:2	adaptive	Once daily oral administrations of SBP-9330 or placebo for 14 consecutive days (Days 1 to 14) under fasting conditions
Additional B4	8:2	adaptive	Once daily oral administrations of SBP-9330 or placebo for 14 consecutive days (Days 1 to 14) under fasting conditions

Each subject will receive once daily oral administration of the assigned treatment and dose under fasting conditions (SBP-9330 or placebo) for 14 consecutive days.

The MAD phase of the study may commence in parallel to the SAD or thereafter. The decision on how early the MAD phase of the study may be started and the doses to be administered will be determined by the Sponsor after consultation with the DSMB based on emerging safety and PK data. The first MAD daily dose will be less than or equal to an already well-tolerated SAD dose for which complete safety and PK data are available.

All relevant safety and available plasma PK data will be reviewed by the DSMB before any dose escalation. The dose levels proposed for MAD cohorts may be adjusted during the course of the study based on preliminary safety and PK data. The dosing frequency may also be changed from once daily to twice daily, without changing the total daily dose outlined in the protocol.

The MAD phase will have a maximum of 4 cohorts. The number of cohorts may be changed at the discretion of the Sponsor depending on the emerging safety and PK data from the previous cohorts. The increase from one dose level to the next dose level will not be more than 3-fold. A MAD daily dose level cannot be higher than the highest dose level tested in SAD.

Subjects will be confined to the CRU from at least 10 hours prior to drug administration until approximately 48 hours after last study drug administration. Subjects will therefore be confined for 17 days and 16 nights (Day -1 to Day 16).

Subjects will return for a follow-up visit approximately 5 days after the last PK blood sample/discharge (Day 21±1).

The schedule of activities of the MAD Phase of the study is described in Table 2.

Altasciences Project Number: CNO-P5-319

#### 3.3.3. Part C - Smoker Phase

Screening of participants will occur within approximately 28 days prior to the first scheduled administration of study medication. Screening data will be reviewed to determine subject eligibility. Subjects who meet all inclusion criteria and none of the exclusion criteria and who consent to participation will be admitted to the CRU for baseline evaluations before dosing (Day -1). All baseline safety evaluation results should be available prior to dosing and continued eligibility confirmed.

Subjects will be randomized to SBP-9330 or placebo in 1 of the 2 planned Smoker cohorts (10 subjects per cohort in 4:1 [SBP-9330:placebo] ratio) to have a total of 8 subjects receiving SBP-9330 and 2 subjects receiving placebo. An additional Smoker cohort (Cohort C3) may be added at the discretion of the Sponsor depending on emerging safety and PK data from previous cohorts.

The proposed Smoker phase design and planned escalation are presented in Table 9.

Cohort	N (active:placebo)	Dose	Drug administrations
C 1	8:2	adaptive	Once daily oral
			administrations for 14
			consecutive days
C2	8:2	adaptive	Once daily oral
			administrations for 14
			consecutive days
Optional C3	8:2	adaptive	Once daily oral
			administrations for 14
			consecutive days

Table 9 Part C - Smoker Phase Design and Dose Levels

Each subject will receive once daily oral administration of the assigned treatment and dose under fasting conditions (SBP-9330 or placebo) for 14 consecutive days.

The Smoker phase of the study may commence after completion of dosing the MAD phase of the study. The Smoker cohort daily dose will be less than or equal to highest MAD dose for which complete safety and PK data are available.

All relevant safety and available plasma PK data will be reviewed by the DSMB before any dose escalation. The DSMB will be provided the randomization code to aide in the review for Part C. The dose levels proposed for Smoker cohorts may be adjusted during the course of the study based on preliminary safety and PK data.

The Smoker phase will have a maximum of 3 cohorts. The number of cohorts may be changed at the discretion of the Sponsor depending on the emerging safety and PK data from the previous cohorts.

Subjects will be confined to the CRU from at least 10 hours prior to drug administration until approximately 48 hours after last study drug administration. Subjects will therefore be confined for 17 days and 16 nights (Day -1 to Day 16).

Subjects will return for a follow-up visit approximately 5 days after the last PK blood sample/discharge (Day 21±1).

Altasciences Project Number: CNO-P5-319

The schedule of activities of the Smoker Phase (Part C) of the study is described in Table 3.

# 3.4. Study Treatments

The following investigational products (IPs) will be administered according to the outlined dose levels in Sections 3.3.1 and 3.3.2.

- Test product: SBP-9330 75-mg, 150-mg and 300-mg capsules
- Placebo: Placebo to match SBP-9330 75-mg, 150-mg and 300-mg capsules

# 3.5. Dose Escalation and Stopping Rules

Escalation to the next higher dose will only proceed if none of the stopping criteria below have been reached and when the safety and tolerability and plasma PK analysis of the previous dose, including delayed emergence of significant AEs in earlier cohorts, are acceptable to the Investigator, Sponsor and DSMB. Dose escalation will be stopped if it is determined that the limits of safety and/or tolerability or the PK stopping criteria (Section 3.5.2) have been reached. This decision will be made by the Sponsor and the Principal Investigator based on DSMB recommendation. If dose escalation is stopped due to any findings, additional cohorts may receive the same or lower doses of the investigational compound. However, in the event that the findings are likely related to  $C_{max}$ , dose escalation may continue by dividing the dose ensuring that the  $C_{max}$  is the same or lower.

## 3.5.1. Individual Subject Stopping Rules

Participation in the clinical study may be discontinued by the Principal Investigator or by the Sponsor for any of the following reasons, but not limited to:

- Any subject experiencing a confirmed drug-related moderate or severe AE or serious AE (SAE) will not receive the next scheduled dose of IP until a safety review of the AE is performed by an Investigator and Sponsor Medical Monitor. The decision to continue dosing must be agreed upon by both an Investigator and Sponsor Medical Monitor.
- Any subject experiencing seizures, intractable headaches, or suicidal ideations.
- Liver chemistry elevations that meet any of the following parameters:
  - ALT or AST  $> 3 \times$  upper limit of normal (ULN) and total bilirubin  $> 2 \times$  ULN without elevated alkaline phosphatase.
  - ALT or AST > 3 × ULN with appearance of fatigue, nausea, vomiting, right upper quadrant pain or tenderness, fever, rash, and/or eosinophilia (>5%).
  - ALT or AST > 8 × ULN, which is confirmed.
- Meets either of the following ECG criteria:
  - QTcF >500 ms
  - QTcF change from baseline >60 ms
  - Subject non-compliance (including any violation of protocol requirements which may affect the study outcome)

Altasciences Project Number: CNO-P5-319

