## 3.5.2. Cohort Stopping Rules

If any of the following safety concerns are observed, dosing of all subjects at the given dose level or higher will be suspended/halted and all available data will be evaluated by the DSMB.

Dose continuation (remaining subjects within a cohort or remaining dosing for a subject) or escalation should not proceed for any of, but not limited to, the following reasons:

- If one SBP-9330-related SAE occurs in a cohort
- Severe AE at least possibly related to SBP-9330 in two or more subjects in the same cohort\*
- Other findings that, at the discretion of the DSMB or Sponsor, indicate further dosing should be stopped

\* Prior to suspending the cohort, if severe AEs are reported in two or more subjects at a given dose level, consideration should be given to the treatment assignment (SBP-9330 or placebo). After causality assessment, the Investigator (or designee) should open the individual randomization code to verify the treatment received. Dosing at the given dose level may continue if only one subject received SBP-9330 and the other(s) received the placebo.

Subjects experiencing severe AEs will be followed up with serial measurements of the related clinical parameter(s), as per medical judgment, until resolution, stabilization, or until the subject is lost to follow-up.

Dose escalation will be discussed during the DSMB meeting and may be stopped depending on Principal Investigator's or Sponsor's decision, based on but not limited to the following:

- New clinically significant abnormalities in physical examination, 12-lead ECG, or vital signs in two or more subjects
- Overall pattern of clinical changes or symptoms that may have appeared minor in terms of an individual AE or subject, but which collectively present a safety concern
- Clinically significant changes in organ-specific laboratory parameters (e.g., liver function enzymes in one or more subjects)
- Pattern of laboratory changes (e.g., a consistent increase or decrease in two or more subjects or within or across dosing cohorts) that might indicate an overall safety concern

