### 7.6.1. Drug-Induced Liver Injury

Abnormal values in aspartate transaminase (AST) and/or alanine transaminase (ALT) concurrent with abnormal elevations in total bilirubin that meet the criteria outlined below in the absence of other causes of liver injury are considered potential cases of drug-induced liver injury (potential Hy's Law cases) and should always be considered important medical events.

Altasciences Project Number: CNO-P5-319

Subjects with AST or ALT and total bilirubin baseline values within the normal range who subsequently present with AST or ALT  $\geq 3$  times the upper limit of normal (3X ULN) concurrent with a total bilirubin  $\geq 2$  X ULN with no evidence of hemolysis and an alkaline phosphatase  $\leq 2$  X ULN or not available, with no other cause for LFT abnormalities identified at the time should be considered to have potentially met Hy's Law. Such potential Hy's Law cases should be reported as SAEs.

Altasciences Project Number: CNO-P5-319

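### The combined transaminase–bilirubin stopping line in Protocol Section 3.5.1 and the potential Hy's Law definition in Section 7.6.1 use different alkaline phosphatase conditions and inequality signs, so some potential Hy's Law SAEs meet none of the liver stopping lines

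*Protocol*

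**What the plan says.** Protocol Section 3.5.1 says that participation "may be discontinued by the Principal Investigator or by the Sponsor for any of the following reasons, but not limited to". One listed reason is "Liver chemistry elevations that meet any of the following parameters", followed by three alternatives:

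- Line 1: ALT or AST > 3 × ULN and total bilirubin > 2 × "ULN without elevated alkaline phosphatase". No ALP number is given.
- Line 2: "ALT or AST > 3 × ULN with appearance of fatigue" or another listed symptom or sign, including rash, fever and eosinophilia. It has no ALP or bilirubin condition.
- Line 3: "ALT or AST > 8 × ULN, which is confirmed". It has no ALP or bilirubin condition.

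Section 7.6.1 covers subjects whose baseline AST or ALT and bilirubin were normal. It requires AST or ALT ≥ 3 × ULN together with bilirubin ≥ 2 "X ULN with no evidence of hemolysis and an alkaline phosphatase" that is ≤ 2 × ULN or not available, and no other cause identified at the time. It then says: "Such potential Hy's Law cases should be reported as SAEs".

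Two SAE provisions also bear on such a case. The first bullet of Section 3.5.1 holds the subject's next dose for a confirmed drug-related SAE until the Investigator and the Medical Monitor have reviewed it and both agree to continue. Section 3.5.2 suspends dosing at that dose level and above on the condition "If one SBP-9330-related SAE occurs in a cohort". Neither has an ALP condition.

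**The concern.** The protocol describes nearly the same laboratory pattern twice, once as a reason to stop a subject and once as an important medical event to be reported as an SAE. One would expect a subject in the second group to be in the first as well, or a stated reason why not. As written, some are not.

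Two things are at stake. The liver lines in Section 3.5.1 work from laboratory values (line 2 adds symptoms or signs) and need no causality judgement, while the SAE provisions do. In addition, Section 3.5 lets escalation proceed only if none of the stopping criteria has been reached, so whether a subject counts as meeting a liver line also enters the escalation decision.

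Timing adds some weight in Parts B and C. Scheduled panels during dosing are pre-dose on Days 1, 3, 7 and 14 (Tables 2 and 3). After a Day 7 sample, the six doses on Days 8 to 13 come before the next scheduled panel, although Section 6.1 allows extra assessments.

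**Working it through.** The plan gives no figure to reproduce. The check is to write both definitions as rules and run cases through them.

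**Rules (all values in × ULN)**

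- Potential Hy's Law (7.6.1): ALT or AST ≥ 3, bilirubin ≥ 2, and ALP ≤ 2 or not available. Baseline AST or ALT and bilirubin are normal, and there is no hemolysis and no other cause.
- Line 1 (3.5.1): ALT or AST > 3, bilirubin > 2, and ALP ≤ c, where c is the unstated cut-off for *elevated*. I took c = 1, 1.5 and 2 as assumptions.
- Line 2 (3.5.1): ALT or AST > 3 with a listed symptom or sign.
- Line 3 (3.5.1): ALT or AST > 8, confirmed.

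**Cases, all assumed to satisfy the other conditions of 7.6.1**

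| Case | ALT or AST | Bilirubin | ALP | Symptoms or signs | Potential Hy's Law | Liver line met |
|---|---|---|---|---|---|---|
| a | 4 | 2.5 | 0.9 | none | yes | line 1 |
| b | 4 | 2.5 | 1.5 | none | yes | none if c = 1; line 1 if c = 2 |
| c | 4 | 2.5 | 1.5 | present | yes | line 2 at any c |
| d | 9, confirmed | 2.5 | 1.5 | none | yes | line 3 at any c |
| e | 4 | 2.5 | missing | none | yes | none can be shown, at any c |
| f | 3 exactly | 2 exactly | 0.9 | none | yes | none, at any c |

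**What the cases show**

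1. The ALP mismatch (case b) affects subjects with ALT or AST above 3 but no confirmed value above 8, bilirubin above 2, no listed symptom or sign, and ALP above c and up to 2. The ALP band has width 2 − c: 2 − 1 = 1 × ULN if c = 1, 2 − 1.5 = 0.5 × ULN if c = 1.5, and 2 − 2 = 0 if c = 2.
2. Missing ALP (case e) does not depend on c. Section 7.6.1 says how to treat it and Section 3.5.1 does not.
3. Exact boundary values (case f) do not depend on c either, because 3.5.1 uses > and 7.6.1 uses ≥. At exactly 3 × ULN, line 2 also fails, since it too uses >.
4. Cases c and d show that lines 2 and 3 catch symptomatic and confirmed > 8 × ULN cases whatever the ALP.

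**The case against.** The strongest reply is that other provisions protect these subjects. A potential Hy's Law case is an SAE. If it is judged related, the first bullet of Section 3.5.1 holds that subject's dosing and Section 3.5.2 suspends dosing at that level and above. Section 7.6.1 already requires that no other cause has been found, so part of the causality judgement has been made by then. The 3.5.1 list is permissive and open-ended, Section 4.3.2 allows withdrawal at any time for a significant safety risk, and Section 3.5.2 names liver enzyme changes in even one subject as a possible ground to stop escalation. A stopping rule and a reporting rule may also differ for good reason. All of this stands and limits the consequences. It does not make the two definitions agree, and every remaining route needs either a causality decision or discretion.

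It is also fair that c = 1 is the ordinary reading of *elevated* and not a stated one. The only ALP number in these provisions is 2 × ULN, in Section 7.6.1. If that is what *elevated* means, case b disappears, but cases e and f remain.

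A reader might infer more than the documents support:

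- *The whole liver rule depends on ALP.* Only one of three alternative lines does.
- *Every subject with the line 1 enzyme and bilirubin values and ALP between 1 × and 2 × ULN is missed.* Lines 2 and 3 catch some of them, and others fail the further conditions of Section 7.6.1 and are not potential Hy's Law cases.
- *The individual and cohort rules contradict each other.* For a related SAE both act; only the liver list is silent.
- *The rat findings show a liver hazard.* Section 1.2.2 reports liver weight increases without histopathologic correlates in the 14-day study. In the nicotine combination study it judges the liver findings, including minimal hypertrophy, to be non-adverse and adaptive, without changes in ALT, AST or GGT.

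**Conclusion.** This is a real internal inconsistency in a safety rule, with partial backstops. It should be corrected, but it does not leave subjects unprotected. The two sections differ on the ALP limit, on missing ALP and on the inequality signs, and an asymptomatic potential Hy's Law case without a confirmed ALT or AST above 8 × ULN can meet none of the liver lines.

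The documents give no liver event rates, so the number of subjects affected cannot be estimated. It is probably small. Missing ALP should be uncommon, because ALP is in the same chemistry panel as ALT, AST and bilirubin (Appendix 6), and exact boundary values are an edge case. The ALP band is the main practical part, and it exists only if *elevated* means a cut-off below 2 × ULN.

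Two further assumptions apply. The example subjects meet the baseline, hemolysis and no-other-cause conditions of Section 7.6.1. I also read *confirmed drug-related* in the first bullet of Section 3.5.1 as covering SAEs as well as other AEs. If it does not cover SAEs, that hold would apply to any SAE, and the practical gap for the individual subject would be narrower. The definitions would still differ.

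**What to change.** Reconcile Protocol Sections 3.5.1 and 7.6.1 on three points:

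- the ALP condition, including what *elevated* means;
- what happens when ALP is not available;
- whether the ALT/AST and bilirubin limits are strict or inclusive.

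If the two definitions are meant to differ, say so and give the reason. Which limits apply is for the sponsor's safety physicians to decide.

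The cost is a short protocol amendment. No new tests are needed, and the SAP restates neither definition. The number of subjects meeting the stopping criterion may change slightly, depending on the limits chosen.
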